13.4.2.1. Treatment States for Adverse Event Data

Treatment State	Definition
Onset Time Since 1 st Dose (Days)	If Treatment Start Date > AE Onset Date = AE Onset Date - Treatment Start Date If Treatment Start Date ≤ AE Onset Date = AE Onset Date - Treatment Start Date + 1 Missing otherwise.
Duration (Days)	AE Resolution Date – AE Onset Date + 1
Drug-related	If relationship is marked 'YES' on eCRF or value is missing.
Onset in Month 1	AE Start Date ≤ Study Day 29
Onset in Months 2 or 3	Study Day 30 ≤ AE Start Date < Study Day 91
Onset after Month 3	AE Start Date ≥ Study Day 91

NOTES:

- If the study treatment stop date is missing then the AE will be considered to be On-Treatment.

13.5. Appendix 5: Data Display Standards & Handling Conventions

13.5.1. Study Treatment & Sub-group Display Descriptors

Treatment Group Descriptions			
RandAll NG		Data Displays for Reporting	
Code	Description	Description	Order ^[1]
A	Tafenoquine 300 mg	TQ+CQ	1
B	Primaquine 15 mg	PQ+CQ	2

NOTES:

- Order represents treatments being presented in TFL, as appropriate.

13.5.2. Baseline Definition & Derivations

13.5.2.1. Baseline Definitions

For all endpoints (except as noted in the additional definitions below) the baseline value will be the latest pre-treatment assessment where treatment is their first dose of study medication (CQ/PQ/TQ/Placebo).

Asexual parasite and gametocyte counts

If there are multiple pre-treatment assessments, a subject will be considered to have a positive (non-zero) baseline count if *any* of the assessments are positive. They will only be considered to have a zero baseline count if all of the pre-treatment assessments are zero.

Pharmacogenetics

The PGx blood draw must be performed at the earliest opportunity after randomisation and during in-clinic treatment (Days 1-3). This will be considered baseline.

Ophthalmic assessments

The last assessment performed on the day of randomisation or earlier will be considered baseline.

13.5.2.2. Derivations and Handling of Missing Baseline Data

Definition	Reporting Details
Change from Baseline	= Post-Dose Visit Value – Baseline
% Change from Baseline	= 100 x [(Post-Dose Visit Value – Baseline) / Baseline]

NOTES:

- Unless otherwise specified, the baseline definitions specified in Section 13.5.2.1 Baseline Definitions will be used for derivations for endpoints / parameters and indicated on summaries and listings.
- Unless otherwise stated, if baseline data is missing no derivation will be performed and will be set to missing.
- The baseline definition will be footnoted on all change from baseline displays.

13.5.3. Reporting Process & Standards

Reporting Process	
Software	

 The currently supported versions of SAS software will be used. 	
Reporting Area	
HARP Server	: UK1SALX00175
HARP Area	: /arenv/arprod/sb252263/taf116564/final
QC Spreadsheet	: \\UK1DSNTV003\SB252263-TAFENOQUINE\Vivax Trt\TAF116564
Analysis Datasets	

 Analysis datasets will be created according to CDISC standards (SDTM IG Version 3.13 & AdaM IG Version 1.0) For creation of ADaM datasets (ADCM/ADAE), the same version of dictionary datasets will be implemented for conversion from SI to SDTM. 	
Generation of RTF Files	

 RTF files will be generated. 	

Reporting Standards	
General	

 The current GSK Integrated Data Standards Library (IDSL) will be applied for reporting, unless otherwise stated: 
 4.03 to 4.23: General Principles 5.01 to 5.08: Principles Related to Data Listings 6.01 to 6.11: Principles Related to Summary Tables 7.01 to 7.13: Principles Related to Graphics 	
Formats	

 All data will be reported according to the actual treatment the subject received unless otherwise stated (see Section 4). GSK IDSL Statistical Principles (5.03 & 6.06.3) for decimal places (DPs) will be adopted for reporting of data based on the raw data collected. Numeric data will be reported at the precision collected on the eCRF. The reported precision from non eCRF sources will follow the IDSL statistical principles but may be adjusted to a clinically interpretable number of DPs, including: 
 Proportions and their Confidence Intervals will be presented to 3 decimal places. Rates and their 95% Confidence Intervals will be presented to 1 decimal place 	
Planned and Actual Time	

 Reporting for tables, figures and formal statistical analyses : 
 Planned time relative to dosing will be used in figures, summaries, statistical analyses and calculation of any derived parameters, unless otherwise stated. The impact of any major deviation from the planned assessment times and/or scheduled visit days on the analyses and interpretation of the results will be assessed as appropriate. Reporting for Data Listings: 
 Planned and actual time relative to study drug dosing will be shown in listings (Refer to 	

Reporting Standards	

IDSL Statistical Principle 5.05.1).
 
 • Unscheduled or unplanned readings will be presented within the subject’s listings. • Visits outside the protocol defined time-windows (i.e. recorded as protocol deviations) will be included in listings but omitted from figures, summaries and statistical analyses. 	
Unscheduled Visits	

 • Unscheduled visits will not be included in summary tables unless they slot into a missing planned visit (see Section 13.3.1) in which case they will be reported as the planned visit. • Unscheduled visits will not be included in figures unless they slot into a missing visit (see Section 13.3.1) in which case they will be reported as the planned visit. • All unscheduled visits will be included in listings. 	
Descriptive Summary Statistics	
Continuous Data	Refer to IDSL Statistical Principle 6.06.1
Categorical Data	N, n, frequency, %
Graphical Displays	

 • Refer to IDSL Statistical Principals 7.01 to 7.13. 	

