Hemoglobin and/or Hct measurements that deviate substantially from previous readings should be immediately repeated via venous sampling. If a significant drop in Hb or Hct is observed upon repeat testing, all additional hematology and clinical chemistry labs should be obtained immediately.

If, after Day 3, platelet counts are $<5 \times 10^4$ per μL , the test should be repeated or confirmed with a manual slide reading.

Table 3 Hematology Tests

Hemoglobin	Hematocrit	Platelets	MCV
WBC	RBC	Reticulocyte	WBC Differential

Table 4 Clinical Chemistry Tests

Creatinine	BUN	Total bilirubin	Indirect bilirubin
AST	ALT	ALP	CPK

Urinalysis will be conducted by local laboratories at screening, Days 3, 5, 8, 11, 15, 22, 29, 60, 90, and 120 (and at the withdrawal and relapse visits if applicable). Urine (approximately 20mL mid-stream urine) will be analyzed for protein, glucose, ketones, bilirubin, blood, nitrites, urobilinogen and leukocyte esterase by dipstick method. Sediment microscopy will be performed if the leukocyte, nitrites, protein, or occult blood is abnormal and will include analysis for white blood cells, red blood cells, hyaline casts, granular casts and cellular casts.

Methemoglobin status will be assessed daily during the in-patient stay, at all out-patient treatment visits (Days 5, 8, 11 and 15) and at selected follow-up visits (Days 22, 29, 60 and 120) as well as at the relapse and withdrawal visits if applicable. Subjects with anemia may have symptomatic methemoglobinemia at levels lower than subjects with normal hemoglobin levels (symptoms typically do NOT occur with MetHb values $<20\%$ in subjects with normal hemoglobin levels).

Ophthalmic assessments will be performed at selected sites prior to randomization then at Days 29 and 90 and at the withdrawal follow-up visit. Assessments will also be carried out at Day 180 (and up to resolution) if the Day 90 assessments show abnormalities. Subjects who do not receive the assessment prior to randomization should not receive any subsequent ophthalmic exams.

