8.2.2. Overview of Planned Clinical Laboratory Analyses

Table 3 provides an overview of the planned analyses, with further details of data displays being presented in Appendix 14: List of Data Displays.

Table 3 Overview of Planned Clinical Laboratory Analyses

Endpoint / Parameter/ Display Type	Absolute			Change from BL		
	Summary		Individual	Summary		Individual
	T	F	L	T	F	L
Chemistry						
Chemistry Data by Treatment and Time	Y	Y ¹				
Chemistry Changes from Baseline				Y	Y	
Chemistry Laboratory Abnormalities ²	Y	Y	Y			
Haematology						
Haematology Data by Treatment, Time and Sex	Y	Y				
Haematology Changes from Baseline by Treatment, Time and Sex				Y	Y	
Haematology Laboratory Abnormalities ²	Y	Y	Y			
Haemoglobin Categories ⁴ of Change from Baseline by Treatment and Time				Y		
Haemoglobin Categories ⁴ of Change from Baseline by Treatment, Time and Sex				Y		
Maximum Fall in Haemoglobin Over First 29 Days ⁴					Y	
Mean Change in Haemoglobin Over First 29 Days ⁴				Y	Y	
Urinalysis						
Urine Concentration			Y			
Urinalysis Dipstick Results	Y		Y			
Hepatobiliary (Liver)						
Liver Monitoring/Stopping Event Reporting	Y		Y			
Liver Biopsy Details	Y		Y			
Liver Imaging Details	Y		Y			
Medical Conditions for Subjects with Liver Stopping Events			Y			

Endpoint / Parameter/ Display Type	Absolute			Change from BL		
	Summary		Individual	Summary		Individual
	T	F	L	T	F	L
LFT Abnormalities		Y				
Maximum LFTs		Y				
LFT Changes from Baseline		Y				

NOTES:

- T = Table, F = Figures, L = Listings, Y = Yes display generated
- Summary = Represents TFL related to any summaries (i.e. descriptive statistics) of the observed raw data.
- Individual = Represents FL related to any displays of individual subject observed raw data.
- ¹ Boxplots by treatment, time and gender for total bilirubin and indirect bilirubin
- ² Abnormalities refer to values outside of the clinical concern range (F3) as defined in Section 13.8.1.
- ³ G6PD enzyme activity only
- ⁴ Categories defined as ≤ 20 g/L, > 20 g/L to ≤ 30 g/L, > 30 g/L
- ⁵ See Section 8.2.2.1
- All scheduled visits should be included in the tables and figures.
- Data recorded at unscheduled assessments will not be included in tables and figures but will be listed.
- Change from baseline is defined in Section 13.5.2.

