13.3. Appendix 3: Assessment Windows

13.3.1. Definitions of Assessment Windows for All Analyses

Visit	Analysis Window	
	Beginning Timepoint	Ending Timepoint
Day 1	Study Day 1	Study Day 1
Day 2	Study Day 2	Study Day 2
Day 3	Study Day 3	Study Day 4
12 hours post randomised treatment ¹	11.5 hours post first dose of randomised treatment (Study Days 1-4)	12.5 hours post first dose of randomised treatment (Study Days 1-4)
Day 5	Study Day 5	Study Day 6
Day 8	Study Day 7	Study Day 9
Day 11	Study Day 10	Study Day 12
Day 15	Study Day 13	Study Day 17
Day 22	Study Day 19	Study Day 25
Day 29	Study Day 26	Study Day 32
Day 60	Study Day 53	Study Day 67
Day 90	Study Day 83	Study Day 97
Day 120	Study Day 110	Study Day 130
Day 150	Study Day 140	Study Day 160
Day 180	Study Day 166	Study Day 201

¹For ECG parameters only

For all data summarised by visit, the nominal visit description will be used. Unscheduled and withdrawal visit data will be slotted into a scheduled visit window, if no competing visit exists within the window. If there are multiple assessments within the same window which are not unscheduled visits, the earliest result will be used in the summaries.

Note that the 12 hours post dose window is used only for the ECG parameters. If there are multiple measurements within the acceptable window, the assessment closest to the nominal visit description will be used in the summaries. If triplicate readings were taken, the mean of the triplicates will be used in the summaries.

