13.6.3. Safety

Clinically Relevant Haemolysis

 • Clinically relevant haemolysis is defined as: a decrease in haemoglobin of $\geq 30\%$ or >30 g/L (>3 g/dL) from baseline; or, an overall drop in haemoglobin below 60 g/L (6.0 g/dL) at any visit after the first dose of study medication. • If a subject has any missing post-baseline haemoglobin data up to Study Day 17, the primary endpoint will be set to missing. • A subject will be classified as not having haemolysis at any visit if they do not meet the above haemoglobin criteria and no visits are missing up to Study Day X. • See Section 13.7.2.3 for further handling of missing data.

ECG Parameters
RR Interval 
 • ECGs are manually read, the RR value preceding the measurement QT interval should be a collected value so no derivation is required.
Corrected QT Intervals 
 • QTcF will be derived at the site and entered into the eCRF.

Adverse Events

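### The RAP's visit rules keep unscheduled Hb results out of the Hb-fall displays, and no rule says whether unscheduled or out-of-window Hb counts toward the primary haemolysis endpoint

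*Supplement*

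**What the plan says.** The plan reviewed is the RAP of 21 February 2017, read with protocol amendment 5.

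- **Out-of-window visits (RAP 13.5.3):** "Visits outside the protocol defined time-windows (i.e. recorded as protocol deviations) will be included in listings but omitted from figures, summaries and statistical analyses". No exception is given. The same section sets the default time basis: "Planned time relative to dosing will be used in figures, summaries, statistical analyses and calculation of any derived parameters, unless otherwise stated".
- **Unscheduled visits, general rule (RAP 13.5.3):** "Unscheduled visits will not be included in summary tables unless they slot into a missing planned visit". Figures have the same rule.
- **Unscheduled laboratory data (RAP 8.2.2, notes to Table 3):** "Data recorded at unscheduled assessments will not be included in tables and figures but will be listed". This is stricter than the general rule.
- **Slotting (RAP 13.3.1):** "Unscheduled and withdrawal visit data will be slotted into a scheduled visit window, if no competing visit exists within the window". For repeated results: "If there are multiple assessments within the same window which are not unscheduled visits, the earliest result will be used in the summaries". The result kept is the earliest, not the lowest.
- **Primary endpoint (RAP 13.6.3):** a qualifying Hb counts "at any visit after the first dose of study medication". Any missing post-baseline Hb up to Study Day 17 makes the endpoint missing. RAP 13.7.2.3 adds a sensitivity analysis that imputes missing data as haemolysis.
- **Source of extra draws (protocol 6.4):** "Hemoglobin and/or Hct measurements that deviate substantially from previous readings should be immediately repeated via venous sampling". Protocol 6.2 also encourages unscheduled visits throughout the 180 days.

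**The concern.** Clinically relevant haemolysis and maximum Hb fall are worst-value measures. One sufficiently low result makes the event, and no normal result elsewhere cancels it. Rules built for tidy by-visit summaries (one value per window, planned visits preferred, deviating visits dropped) do not suit such measures.

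The values at risk are not a random sample. Unscheduled draws are often taken because the subject has symptoms or Hb is already suspected of falling. Leaving them out can only lower the recorded maximum fall, and can only lower the event count in a subject otherwise classed as event-free.

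Haemolysis in all subjects is the only primary endpoint left after the RAP dropped the G6PD-deficient subgroup estimate, and RAP 7.1.2 expects its incidence to be low. With few events, one classification is visible in the result. Two programmers following this RAP in good faith could report different primary counts, and a choice made after unblinding would be open to challenge.

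**Working it through.** **1. Does the primary derivation override the general rules?** It does not say so. The authors wrote exceptions where they wanted them: RAP 13.6.2 waives windows for the PK compliance samples, the relapse definition in RAP 13.6.4 covers every assessment up to Study Day 201, and protocol 8.3.4 brings extra-visit data into time to relapse. Haemolysis has no matching sentence. Its derivation also still holds an unfilled placeholder (Study Day X), so a deliberate override is hard to infer from it.

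**2. Which draws can drop out?** The windows in RAP 13.3.1 leave these study days in no haematology window after first dose:
- Day 2 (no haematology scheduled) and Day 18;
- Days 33–52, 68–82, 98–109, 131–139 and 161–165.

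A draw on such a day has no planned visit to fill. A draw inside a window fills it only if no planned visit competes.

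**3. A case that is lost.** Suppose the planned Day 8 Hb is 10.0 g/dL and an unscheduled draw the next day gives 6.8 g/dL. Both lie in the Day 8 window (Study Days 7–9).
- No event at 10.0: the fall must not exceed 3 g/dL, so baseline ≤ 13.0; the fall is then 3.0/13.0 = 23%, below 30%.
- Event at 6.8: a fall of at least 30% needs baseline ≥ 6.8/0.7 = 9.71.

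For baselines from about 9.7 to 13.0 g/dL the event rests on the unscheduled draw alone, unless a later planned Hb also qualifies.

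**4. The plan's own precision figures (protocol 8.2.1).** Half-width = 1.96·√(p(1−p)/n):
- p = 0.50: n = 30 gives 17.9%, n = 15 gives 25.3% (stated 18%, 25%);
- p = 0.08: n = 200 gives 3.8%, n = 100 gives 5.3% (stated 4%, 5%).

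They reproduce, but they assume that every event is counted.

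**5. Effect of one lost event.** The meta-analysis plan gives 251 randomised at 2:1. I assume 167 and 84. One event is 1/167 = 0.6 points on tafenoquine (TQ) or 1/84 = 1.2 points on primaquine (PQ). With the Newcombe interval of RAP 7.1.2, and event counts that are assumptions:

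| TQ v PQ | Difference (points) | 95% CI |
|---|---|---|
| 4/167 v 2/84 | 0.01 | −6.05 to 4.01 |
| 4/167 v 1/84 (one PQ event lost) | 1.20 | −4.24 to 4.94 |
| 3/167 v 2/84 (one TQ event lost) | −0.58 | −6.59 to 3.18 |

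At the protocol's 8% rate, 16/200 v 8/100 gives 0.0 (−7.6 to 6.0), and losing one TQ event gives −0.5 (−8.1 to 5.4).

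**The case against.** A reader might infer that the RAP excludes unscheduled Hb from the primary endpoint outright. The documents do not support that. The sentence on out-of-window visits concerns visits recorded as protocol deviations, and a triggered safety draw is not one. The unscheduled-visit rule in 13.5.3 names tables and figures, not statistical analyses. The slotting text in 13.3.1 concerns data summarised by visit, and the note in 8.2.2 belongs to the secondary laboratory displays. The wording of 13.6.3 can fairly be read as overriding all of these. This stands: for the primary endpoint the defect is an unresolved conflict. It does not remove the problem, because the primary result is itself a table and a figure (Table 3.1, Figure 3.1) and nothing tells the programmer which rule governs.

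Nor is every route a loss. A repeat that follows a planned value already over the threshold adds no event. If omission of an out-of-window planned visit up to Day 17 is treated as missing data, the subject becomes missing in the primary analysis and a haemolysis case in the sensitivity analysis, not event-free. Planned haematology is frequent (Days 3, 5, 8, 11, 15, 22 and 29), so Hb must recover above the threshold before the next planned draw for an event to vanish. Falls in the first 15 days are also protocol-defined SAEs, and all unscheduled results are listed. These points narrow the exposure. They do not cover an event seen only at an unscheduled draw with every planned visit attended, or one seen only outside the windows after Day 17. SAE tables and listings do not correct the primary estimate.

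**Conclusion.** The point holds in two parts of different strength. For the maximum-fall and Hb-decline displays, the exclusion of unscheduled values is what 8.2.2 says. For the primary endpoint, loss of an event is possible on a literal reading but not certain, because 13.6.3 conflicts with 13.5.3 and neither yields expressly.

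The size is unknown. The documents give neither an expected number of off-schedule draws nor the share of events seen only there. The shifts of 0.6 and 1.2 points per event rest on an assumed 167:84 split, and the intervals on assumed event counts. The between-arm difference can move either way, depending on which arm loses the event. No hypothesis or margin is tested, so no formal decision changes; what is exposed is the accuracy and reproducibility of the primary safety estimate. Given how small the remedy is, it should be settled before unblinding.

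**What to change.** Add to RAP 13.6.3, with matching exceptions in 13.5.3 and 8.2.2:

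- Clinically relevant haemolysis and maximum Hb fall are derived from all Hb results after the first dose: scheduled, unscheduled, relapse, withdrawal and out-of-window.
- Visit windowing and one-result-per-window selection apply only to by-visit summaries.
- A draw made outside its window counts as a result when judging whether a subject is evaluable to Study Day 17.

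The cost is a few lines of RAP text and a change to the derivation step for the endpoint and the Hb-fall displays. It uses data already collected.

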13.6. Appendix 6: Derived and Transformed Data

13.6.1. General

Multiple Measurements at One Time Point

- If there are multiple assessments within the same window which are not unscheduled visits, the earliest result will be used in the summaries. All values will be listed. For ECGs, if there are multiple assessments at the same visit, the mean will be derived and used in any derivation of summary statistics but if listed, all data will be presented.
- Subjects having both High and Low values for Normal Ranges at any post-baseline visits for safety parameters will be counted in both the High and Low categories of “Any visit post-baseline” row of related summary tables. This will also be applicable to relevant Potential Clinical Importance summary tables.

Study Day

- Calculated as the number of days from the date of the Study Day 1 (first dose of study medication including CQ):
 - Ref Date = Missing → Study Day = Missing
 - Ref Date < Date of Study Day 1 → Study Day = Ref Date – Date of Study Day 1
 - Ref Date ≥ Date of Study Day 1 → Study Day = Ref Date – (Date of Study Day 1) + 1
- Study Day 180 refers to a time point exactly 179 days after Study Day 1 (when the first dose of study medication including CQ was taken), whereas the ‘Day 180 visit’ refers to the nominal Day 180 assessments which did not necessarily occur on Study Day 180.

13.6.2. Study Population

Demographics

Age

- Only the year of birth is collected in the eCRF and the day and month are imputed as ‘30th June’.
- GSK standard IDSL algorithms are used to calculate age at baseline.
- Birth date will be presented in listings as ‘YYYY’.
- Age on the date of first dose will be calculated in years.

Prior and Concomitant Medications

- Medications will be coded using the latest version of GSK Drug.
- Prior medications = medications taken up to 30 days before the date and time of the first dose of study medication.
- Any medications with stop dates earlier than 30 days will not be reported in tables and listings.
- Concomitant medications = medications with start date and time on or after the start date and time of the first dose of study medication (Study Day 1).
- See Section [13.7.2](#) for the handling of missing and partial dates.

Treatment Compliance and Exposure

- For the first three days of the study, all study medication will be administered in the presence of the Investigator or study nurse, and ingestion confirmed.
- On any day of in clinic dosing, a subject will be classified as compliant with daily administered dose if they do not vomit the initial dose or if they are successfully re-dosed.
- A subject is considered to be compliant in clinic if they retain all study medication given to them on all three days of dosing.
- Subjects will also take PQ or PQ placebo on Study Days 4 to 15, where administration is not directly observed (with the exception of G6PD-deficient subjects, who will receive directly-observed therapy on all 15 days).
- A patient will be considered to be compliant as an outpatient if their final pill count data shows they took at least 12 doses of PQ or PQ placebo.
- Compliance will also be determined using the Day 8 and Day 15 PK samples i.e. a quantifiable amount of carboxyPQ from samples taken at the Day 8 and Day 15 visits. No assessment windows will be applied.
- Subjects who were randomized but did not report a treatment start date will be categorised as having zero doses.
- Treatment stop dates are not recorded so duration of exposure will not be calculated.

G6PD enzyme activity as a percentage of site median

- Each site has a median G6PD enzyme value for healthy G6PD-normal subjects, determined from G6PD-normal males in study TAF115226:

Region	Country	Site	Investigator	Centre ID	G6PD median value (IU/g Hb)
South America	Brazil	Manaus	[name]	PPD	7.92
	Peru	Iquitos	[name]		9.01
	Colombia	Monteria	[name]		8.32
	Colombia	Cali	[name]		7.17
Asia	Thailand	Bangkok	[name]	PPD	7.40
	Thailand	Umphang	[name]		8.16
	Thailand	SMRU Shoklo Malaria Research Unit	[name]		7.79
	Vietnam	Ho Chi Minh City	[name]		8.38

- Enzyme activity as percentage of site median = (absolute enzyme activity / site median) x 100%

